16.3 Analysis on Subgroups

Subgroups for analysis are defined in Section 10. The analysis of the primary endpoint (number of progression free subjects at week 12) and PFS and OS will be presented by subgroups.

16.4 Other Endpoint Analyses

Analysis Set: ITT/SAF

16.4.1 Endpoint Analysis per Independent Endpoint Review Committee (IERC)

The PFS, TTP, and BOR per IERC for both RECIST 1.1 and mRECIST will be calculated as a sensitivity analysis to the primary and secondary endpoints. In case of different dates of scans within the same tumor assessment visit, the earliest scan date should be used as the date of tumor assessment.

Overall summary tables per the IERC for both RECIST 1.1 and mRECIST will be produced for PFS and TTP as described in Sections 16.2.1 and 16.2.2, respectively.

Contingency tables for both RECIST 1.1 and mRECIST will be created to compare the following tumor assessment results between IERC and investigators:

• BOR (NE / PD / SD / CR / PR / Non-CR/non-PD / CR + PR)

16.4.2 Sum of Longest Diameters (SOLD)

The sum of longest diameters (SOLD) of viable target lesions is collected on the "Sum of Longest Diameters" eCRF page. The relative change in SOLD of target lesions from baseline will be calculated as follows:

((SOLD of the target lesions at post-baseline – SOLD of target lesions at baseline) / SOLD of target lesions at baseline) *100

The relative change from baseline of SOLD in target lesions as well as occurrence of initial progressive disease with rationale evaluation type (target lesion/non-target lesion/new lesion) will be displayed against time point (weeks since treatment initiation) in spider plots. The baseline relative change is considered "0" on day 1. One plot will be color coded for c-Met status (IHC) and one will be color coded for c-Met status (ISH). Reference lines at +20% and -30% will be shown.

Best relative change in SOLD of target lesions from baseline will be calculated as follows for all subjects that present a measurable tumor at baseline and at least one post-baseline tumor assessment:

((the lowest SOLD of target lesions at post-baseline – SOLD of target lesions at baseline) / SOLD of target lesions at baseline) *100

The best relative change from baseline in SOLD will be displayed using waterfall plots. One plot will be color coded for c-Met status (IHC) and one will be color coded for c-Met status (ISH). Reference lines at +20% and -30% will be shown.

Summary statistics for the SOLD values and their change from baseline over time will be presented.

If sufficient HGF data is available, scatter plots of baseline HGF (both CAF and cytoplasmic) versus the best (minimum) on treatment SOLD value will be presented.

SOLD data including absolute and relative change from baseline values will be listed.

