#### Measurable Disease

Tumor lesions: Must be accurately measured in at least one dimension (longest diameter in the plane of measurement is to be recorded) with a minimum size of:

- 10 mm by CT scan (irrespective of scanner type) and MRI (no less than double the slice thickness and a minimum of 10 mm)
- 10 mm caliper measurement by clinical exam (when superficial)
- 20 mm by chest X-ray (if clearly defined and surrounded by aerated lung)

*Malignant lymph nodes*: To be considered pathologically enlarged and measurable, a lymph node must be  $\geq 15$  mm in short axis when assessed by CT scan (CT scan slice thickness recommended to be no greater than 5 mm). At baseline and in follow-up, only the short axis will be measured and followed.

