16.2.1.5 Sum of Longest Diameters (SOLD)

The sum of longest diameters of viable target lesions is collected on the "Sum of Longest Diameters" eCRF page. The relative change in SOLD of target lesions from baseline will be calculated as follows:

((SOLD of the target lesions at post-baseline – SOLD of target lesions at baseline) / SOLD of target lesions at baseline) *100

The relative change from baseline of SOLD in target lesions as well as occurrence of initial progressive disease with rationale evaluation type (target lesion/non-target lesion/new lesion) will be displayed against time point (weeks since treatment initiation) in a spider plot. The baseline relative change is considered "0" on day 1. Dose level and c-Met status (IHC/ISH) will be distinguished by different colors, line types, and/or symbols. Reference lines at +20% and -30% will be shown.

Best relative change in SOLD of target lesions from baseline will be calculated as follows for all subjects that present a measurable tumor at baseline and at least one post-baseline tumor assessment:

((the lowest SOLD of target lesions at post-baseline – SOLD of target lesions at baseline) / SOLD of target lesions at baseline) *100

The best relative change from baseline in SOLD will be displayed using waterfall plots. One plot will be color coded for dose level and c-Met status (IHC) and one will be color coded for dose level and c-Met status (ISH). Reference lines at +20% and -30% will be shown.

Summary statistics for the SOLD values and their change from baseline over time will be presented by the following in separate tables:

- Dose level and overall
- c-Met status (IHC), dose level, and overall
- c-Met status (ISH), dose level, and overall

If sufficient HGF data is available, scatter plots of baseline HGF (both CAF and cytoplasmic) versus the best (minimum) on treatment SOLD value by dose level will be presented.

SOLD data including absolute and relative change from baseline values will be listed.

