16.2.7 Biological Response

Biological response is defined as the proportion of subjects with a decrease in AFP level of more than 20% at the Cycle 3 assessment, or the last assessment for subjects that terminated treatment prior to the Cycle 3 assessment, as compared with baseline. AFP level is measured at screening, Cycle 1 Day 1 (only if the screening measurement was done more than 7 days prior), Day 1 of every cycle thereafter for which there is a visit, and the End of Treatment visit.

Biological response will be summarized, including corresponding two-sided exact Clopper-Pearson (2) 90% CIs.

If sufficient HGF data is available, scatter plots of best (minimum) on treatment AFP value versus both baseline HGF (CAF and cytoplasmic) will be provided.

Biological response will be flagged on the tumor marker listing. (See Section 17.3.)

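### The planned scatter plots of baseline tumour HGF use the raw minimum SOLD or AFP, so they mix HGF's relation to baseline level with its relation to response

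*SAP*

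**What the plan says.** Four plots are affected, two in each SAP. All are conditional on sufficient HGF data.

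- Phase II SAP 16.4.2: baseline HGF, CAF and cytoplasmic, "versus the best (minimum) on treatment SOLD value will be presented".
- Phase II SAP 16.2.7: "scatter plots of best (minimum) on treatment AFP value versus both baseline HGF (CAF and cytoplasmic) will be provided". Phase Ib SAP 16.2.1.6 has the same sentence.
- Phase Ib SAP 16.2.1.5: baseline HGF "versus the best (minimum) on treatment SOLD value by dose level will be presented".

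The word *value* means the raw measurement. Phase II SAP 16.4.2 separates values from changes: "Summary statistics for the SOLD values and their change from baseline over time will be presented". None of the four plots is expressed as change, stratified by baseline or adjusted for it.

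The same sections measure response relative to baseline elsewhere. For SOLD: "The best relative change from baseline in SOLD will be displayed using waterfall plots", and for those plots "Reference lines at +20% and -30% will be shown". For AFP: "Biological response is defined as the proportion of subjects with a decrease in AFP level of more than 20% at the Cycle 3 assessment", compared with baseline. The AFP line plots in Phase Ib SAP 16.2.1.4 and Phase II SAP 16.2.5 also use percent change. In the visible text, none of these relative measures is plotted against HGF.

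**The concern.** The lowest SOLD reached on treatment is a within-subject best, but it is not comparable between subjects who start from different tumour sizes. A large tumour that responds can have a higher minimum than a small tumour that progresses. The same holds for AFP, where the quantity that gets in the way is the AFP level at entry.

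HGF is a plausible predictor in this programme. Protocol 3.4 reports that liver cancer explants with high HGF/c-Met were sensitive to the drug, while those with moderate or low levels were not. A reader will look to these plots for the same pattern in patients. If HGF is related to baseline SOLD or AFP, that relation alone produces a slope, and an upward slope would read as resistance. If HGF is truly related to shrinkage, the spread in baseline blurs it. Both SAPs (section 5) say the planned analyses will go into submissions or manuscripts, so a misleading plot could travel beyond the trial report.

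**Working it through.** **No stated figure is in dispute.** The Phase II sample size only sets the maximum number of points. It reproduces: with 48 subjects and rejection at 12 or more, the exact one-sided alpha is 0.0478 at a true rate of 15%, and power is 0.8186 at 30%.

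**Step 1, from the documents' own limits.** The two reference lines differ by a factor of 1.20/0.70 = 1.71. Baseline SOLD can vary far more. Protocol Appendix J sets the smallest measurable non-nodal lesion at "10 mm by CT scan (irrespective of scanner type) and MRI", and it allows up to five target lesions with no upper size limit. An example:

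- Baseline 150 mm, shrinking 30% (partial response): minimum 150 × 0.70 = 105 mm.
- Baseline 20 mm, growing 25% at the first scan (+5 mm, so progression under Appendix J): minimum 20 × 1.25 = 25 mm.

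The planned plot puts the progressor far below the responder, which is the better end of the axis.

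**Step 2, share of variance due to baseline.** Write log(minimum) = log(baseline) + log(best ratio) and take the two terms as independent, with standard deviations *sb* and *sc*. Then the baseline share is sb²/(sb² + sc²). The largest possible correlation of a perfect HGF-response relation with the plotted value is sc/√(sb² + sc²). All standard deviations here are assumptions.

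- SOLD, sb = 0.4, sc = 0.40: 0.16/0.32 = 50%; maximum correlation 0.71.
- SOLD, sb = 0.4, sc = 0.35: 0.16/0.2825 = 57%; maximum correlation 0.66.
- SOLD, sb = 0.6, sc = 0.25: 0.36/0.4225 = 85%.
- SOLD, sb = 0.8, sc = 0.15: 0.64/0.6625 = 97%; maximum correlation 0.18.
- AFP, sb = 1.5, sc = 1.5: 2.25/4.50 = 50%.
- AFP, sb = 3.0, sc = 0.5: 9/9.25 = 97%.

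These shares are on the log scale, and the SAPs specify no log axis. On the raw scale, simulation gives 46-92% for SOLD (sb 0.4-0.8, sc 0.2-0.4). For AFP (sb 1.5-3.0, sc 0.5-1.5) it gives 13-96%, which is unstable because a few extreme values dominate.

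**Step 3, what the SOLD plots would show.** Simulation with 400,000 draws, sb 0.4-0.8, sc 0.2-0.4. The entries are correlations of HGF with the plotted variable; a negative sign means that higher HGF goes with a lower plotted value.

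| True situation | Raw minimum (planned) | Best relative change |
|---|---|---|
| HGF correlates −0.5 with log best ratio, 0 with baseline | −0.10 to −0.32 | −0.48 to −0.50 |
| HGF correlates +0.4 with baseline, 0 with response | +0.26 to +0.34 | 0.00 |
| Both of the above | −0.06 to +0.22 | −0.48 to −0.50 |

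In the third row the association is lost or reversed.

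No test is planned, but power indicates how visible a pattern would be. With n = 48, one-sided 5% and the Fisher transformation, power = Φ(atanh|r|·√45 − 1.645). This is 0.98 at r = −0.5, 0.44 at −0.22 and 0.29 at −0.16. The last two are the log-scale dilutions at sb = 0.6 with sc = 0.3 and 0.2.

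**Step 4, AFP.** A true correlation of −0.5 with the log ratio appears as 0.00 to −0.11 against the raw minimum, −0.08 to −0.36 against the log minimum, and −0.25 to −0.47 against percent change. The log ratio keeps the −0.5 by construction.

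**The case against.** The strongest case on the other side concerns scope and weight.

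- **Other HGF analyses exist.** Phase II SAP 10.2 defines subgroups by CAF, cytoplasmic and circulating HGF, and 16.3 presents the primary endpoint, PFS and OS by subgroup. This stands, so a reader who inferred that these plots are the trial's only look at HGF and outcome would be wrong. The subgroups do not cover depth of shrinkage or AFP change, and the visible Phase Ib text has no counterpart. Parts of both SAPs are blacked out and may hold further HGF analyses.
- **The plots are not empty.** A reader might infer that they cannot show any HGF-response relation. The working does not support that: a perfect relation would still correlate 0.18 to 0.71 with the minimum SOLD. The accurate description is diluted and confounded.
- **The sizes are assumed.** No document gives a standard deviation for SOLD, AFP or their changes, and independence of baseline and change is also assumed. That baseline dominates is likely but not established; in the least favourable SOLD case the share is about half.
- **HGF is not the selection marker.** Protocol 5.2.2 speaks of c-Met alterations only. For c-Met, the SAPs do use relative SOLD change, in the spider and waterfall plots.
- **Little depends on the plots.** They are conditional, descriptive, untested and linked to no decision. Relative SOLD change is listed per subject, so the better SOLD plot could be made afterwards.
- **Percent change in AFP has its own fault.** It is unstable at low baseline AFP, and such subjects are included (the group below 200 IU/mL). This stands and shapes the fix.

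These points limit the weight of the concern. None is a reason to prefer the raw minimum.

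**Conclusion.** The concern holds as a minor, exploratory point, and correcting it is a free improvement. In all four plots the vertical variable carries the baseline level, so a pattern cannot be attributed to response. That much follows from the text and from the identity minimum = baseline × best ratio. The size rests on assumption: about 50-97% of the variance of log minimum SOLD for *sb* of 0.4-0.8 and *sc* of 0.15-0.40, with baseline and change independent. For AFP the share is 50-97% on the log scale and has no stable value on the raw scale. The confounder is baseline SOLD in one pair of plots and baseline AFP in the other; tumour burden should not be read as the explanation for both. No primary or secondary conclusion is affected.

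**What to change.** In Phase Ib SAP 16.2.1.5 and 16.2.1.6 and Phase II SAP 16.2.7 and 16.4.2, change the plotted variable:

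- SOLD: baseline HGF (CAF and cytoplasmic) against best relative change from baseline, as already derived for the waterfall plots.
- AFP: baseline HGF against best change from baseline, preferably log(minimum/baseline), because percent change is unstable when baseline AFP is low.
- If the raw-minimum plot is kept, show it only as a supplement with each subject's baseline marked.

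The cost is one sentence per section and a change of plotted variable, with no new data. One detail needs stating for the log ratio: Phase Ib SAP 17.3 imputes laboratory values below the detection limit as half that limit, but Phase II SAP 17.3 gives no such rule, so the Phase II text should say how such AFP values are handled.

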16.4.3 Health-related Quality of Life

Health-related quality of life will be assessed using the FHSI-8 and FACT-HP questionnaires. The data are collected on the "FHSI-8" and "FACT-HP" eCRF pages, respectively.

16.4.3.1 Functional Assessment of Cancer Therapy Hepatobiliary Symptom Index 8 (FHSI-8)

FHSI-8 data will be summarized descriptively at baseline and at all scheduled administrations of the questionnaire during the study. FHSI-8 data values range from 0 to 32, with a higher score indicating better quality of life. The data is scored as described in the guidelines in Appendix 2. Changes in FHSI-8 scores from baseline will be summarized by visit. The percentage of subjects missing assessments will be summarized for each scheduled administration of the questionnaires. A listing including FHSI-8 data will be provided. Changes from baseline indicative of deterioration of symptoms (a decrease in overall score of greater than or equal to 4) will be flagged in the listing. The FHSI-8 is presented in Appendix E of the CTP.

16.4.3.2 Functional Assessment of Cancer Therapy-Hepatobiliary (FACT-HP)

FACT-HP data includes, in addition to the generic core (FACT-G), an 18-item module that addresses specific aspects of hepatobiliary cancer. The objective of the FACT-G is to measure health-related quality of life of people with chronic illnesses through 27 items across 4 domains: physical well-being (PWB), social/family well-being (SWB), emotional well-being (EWB), and functional well-being (FWB). The FACT-HP adds 18 items related to disease-specific issues. The FACT-HP questionnaire will be scored by the FACT-Hep scoring guidelines (Version 4.0) in Appendix 3. All FACT-HP scales are scored so that a higher score represents better quality of life. The abbreviations FACT-HP and FACT-Hep both refer to the Functional Assessment of Cancer Therapy – Hepatobiliary questionnaire. The FACT-HP abbreviation is used in the CTP whereas FACT-Hep is used in the scoring guidelines as seen in Appendix 3.

[figure not shown]
Descriptive statistics for FACT-HP scores and changes from baseline will be summarized at all scheduled administrations of the questionnaires during the study. These scores will include the following:

- FACT-G total score
- FACT-Hep total score
- FACT-Hep Trial Outcome Index (TOI)
- PWB subscore
- SWB subscore
- EWB subscore
- FWB subscore
- Hepatobiliary Cancer Subscale score

The percentage of subjects missing assessments will be summarized for each scheduled administration of the FACT-HP questionnaire. A listing including the PWB, SWB, EWB, FWB, and hepatobiliary cancer subscale, FACT-G total, FACT-Hep total, and FACT-Hep TOI scores will be provided. The FACT-HP is presented in Appendix F of the CTP.

17 Safety Evaluation

Analysis Set: ITT/SAF

The subsections in this section include specifications for summarizing safety endpoints that are common across clinical trials such as AEs, laboratory tests and vital signs.

17.1 Adverse Events

Adverse Event definitions:

• Treatment emergent adverse events: A treatment emergent adverse event (TEAE) is defined as an adverse event with a start date on or after the date of first dose of tepotinib and up to 33 days after the last treatment administration (the last possible day for the end of trial visit) unless considered drug treatment-related by the investigator, in which case it is classified as a TEAE despite occurring more than 33 days after the last treatment administration. If the onset date of the AE is the same as the date of the first dose, the AE

will not be regarded as treatment-emergent if the onset of the AE was before first study drug administration (according to the information provided on the AEs CRF page).

- Serious Adverse Events (SAE): serious adverse events (as recorded on the "Adverse Event Details" eCRF page, Serious Adverse Event = Yes).
- **Related Adverse Events:** adverse events with relationship to study treatment (as recorded on the "Adverse Event Details" eCRF page, Relationship with study treatment = Related) reported by the investigator and those of unknown relationship (i.e. no answer to the question "Relationship with study treatment").
- Adverse Events Leading to Treatment Discontinuation: adverse events leading to permanent discontinuation of study treatment (as recorded on the "Adverse Event Details" eCRF page, Action taken with study treatment = Drug withdrawn).
- Adverse Events Leading to Death: adverse event leading to death (as recorded on the "Adverse Event Details" eCRF page, Outcome = Fatal, as well as AEs of Grade 5).
- Adverse Events of Special Interest (AESI): adverse events of special interest (amylase increase ≥ grade 3 or lipase increase ≥ grade 3)

All analyses described in Section 17.1 will be based on TEAEs if not otherwise specified. The AE listing will include all AEs (whether treatment-emergent or not). A listing of AESIs will also be provided.

In AE listings, a flag will indicate whether the AE occurred before, during, or after the treatment emergent period.

Incomplete AE-related dates will be handled as follows:

- In case the onset date is missing completely or missing partially but the onset month and year, or the onset year are equal to the start of trial treatment then the onset date will be replaced by the minimum of start of trial treatment and AE resolution date.
- In all other cases the missing onset day or missing onset month will be replaced by 1.
- Incomplete stop dates will be replaced by the last day of the month (if day is missing only), if not resulting in a date later than the date of subject's death. In the latter case, the date of death will be used to impute the incomplete stop date.
- In all other cases the incomplete stop date will not be imputed. If stop date of AE is after date of cut-off outcome of AE is ongoing at cut-off.
- Further information after cut-off (like fatal outcome) might be taken from Safety database and included separately into CTR.

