# 7.4.1.3 Definition of the Adverse Event Reporting Period

The AE reporting period for safety surveillance begins when the subject is included into the trial (date of first signature of informed consent) and continues through the trial's Post-treatment Follow-up visit, as described in Section 7.1.5. If the Post-treatment Follow-up Visit was not performed (e.g., the subject could not come back to the site for a visit), a telephone interview should be performed to document any AEs that occurred in this time period.

Any SAE assessed as related to MSC2156119J must be reported whenever it occurs, irrespective of the time elapsed since the last administration of MSC2156119J.

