#### 8.5.4 Safety Analyses

Any treatment emergent AEs will be summarized, i.e., those events that are emergent during treatment having been absent pretreatment, or worsen relative to the pretreatment state and with onset dates occurring within the first dosing day of study treatment until 33 days after the last dose of study treatment. No formal statistical comparisons are planned.

The extent of exposure to MSC2156119J will be characterized by time on treatment, number of initiated and completed cycles, actual cumulative dose (mg) and compliance (%).

AEs will be coded according to the Medical Dictionary for Regulatory Activities (MedDRA). Severity of AEs will be graded using NCI-CTCAE (Version 4.0) toxicity grade. The incidence of treatment-emergent AEs, SAEs, related AEs and SAEs, AEs of Grade  $\geq$  3 by NCI-CTCAE, related AEs of Grade  $\geq$  3 by NCI-CTCAE, AEs leading to permanent treatment discontinuation will be summarized by MedDRA system organ classes and preferred terms. AE summaries will be prepared for Cycle 1 and the whole treatment period.

All deaths and deaths within 33 days after last dose of study treatment as well as reasons for death will be tabulated.

Descriptive summaries of actual (absolute) laboratory values and changes from baseline will be presented. Laboratory results will be classified by grade according to NCI-CTCAE, Version 4.0. The worst on-treatment grades after the first dose of trial treatment will be summarized. Shifts in NCI-CTCAE grades from baseline to worst on-treatment grade and from baseline to end of treatment (day of final dose of MSC2156119J) will be presented.

Changes from baseline to minimum and maximum on-treatment values will be summarized descriptively for vital signs (body temperature, heart rate, and blood pressure) and body weight. Similarly, change from baseline to worst on-treatment value will be summarized descriptively for the QTc interval.

Clinically significant, abnormal findings from 12-lead ECG during treatment phase will be descriptively presented.

The baseline results of the physical examination will be presented. Clinically significant, abnormal findings from the physical examination are to be reported as AEs. Separate summaries of the physical examination during and after treatment will not be provided.

The ECOG performance score will be summarized descriptively by visit.

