17.1 Adverse Events

Adverse Event definitions:

- Treatment emergent adverse events (TEAEs): A TEAE is defined as an adverse event with a start date on or after the date of first dose of tepotinib and up to 33 days after the last treatment administration (the last possible day for the end of trial visit) unless considered drug treatment-related by the investigator, in which case it is classified as a TEAE despite occurring more than 33 days after the last treatment administration. If the onset date of the AE is the same as the date of the first dose, the AE will not be regarded as treatment-emergent if the onset of the AE was before first study drug administration (according to the information provided on the AEs CRF page).
- Serious Adverse Events (SAE): serious adverse events (as recorded on the "Adverse Event Details" eCRF page, Serious Adverse Event = Yes).
- **Related Adverse Events:** adverse events with relationship to study treatment (as recorded on the "Adverse Event Details" eCRF page, Relationship with study treatment = Related) reported by the investigator and those of unknown relationship (i.e. no answer to the question "Relationship with study treatment").

- Adverse Events Leading to Treatment Discontinuation: adverse events leading to permanent discontinuation of study treatment (as recorded on the "Adverse Event Details" eCRF page, Action taken with study treatment = Drug withdrawn).
- Adverse Events Leading to Death: adverse event leading to death (as recorded on the "Adverse Event Details" eCRF page, Outcome = Fatal, as well as AEs of Grade 5).
- Adverse Events of Special Interest (AESI): adverse events of special interest (amylase increase ≥ grade 3 or lipase increase ≥ grade 3)

All analyses described in Section 17.1 will be based on TEAEs if not otherwise specified. The AE listing will include all AEs (whether treatment-emergent or not). A listing of adverse events of special interest (AESIs) will also be provided.

In AE listings, a flag will indicate whether the AE occurred before, during, or after the treatment emergent period.

Incomplete AE-related dates will be handled as follows:

- In case the onset date is missing completely or missing partially but the onset month and year, or the onset year are equal to the start of trial treatment then the onset date will be replaced by the minimum of start of trial treatment and AE resolution date.
- In all other cases the missing onset day or missing onset month will be replaced by 1.

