8.1 Sequence of Analyses

The final analysis will be performed at the end of the trial, 12 months after the last subject's first dose of tepotinib. The final analysis will occur once all trial data is in-house, all data queries are resolved, and the database is fully locked.

9 Changes to the Planned Analyses in the Clinical Trial Protocol

The following are changes to the planned analyses in the clinical trial protocol:

- Physical examination results at baseline will not be presented since these are not collected on the eCRF. Relevant findings had to be entered on the medical history or adverse event eCRF page.
- Relative dose intensity will be summarized rather than treatment compliance.
- The Pd Analysis Set is not defined in this SAP since all Pd related analyses will be carried out on the intent-to-treat (ITT)/safety (SAF) analysis set.
- The deterioration of symptoms assessed by FHSI-8 is defined in accordance with the scoring guidance in appendix 2 as at least a 4-point decrease compared with the baseline value.
- Summaries of sum of longest diameter (SOLD) data are included but these are not explicitly mentioned in the protocol.
- Summaries of quality of life data are included but these are not explicitly mentioned in the protocol.
- Duration of response will be calculated and presented in data listings but this is not explicitly mentioned in the protocol.
- The underlying disease or medical condition related to etiology subgroups will be hepatitis C virus (HCV), and other as opposed to hepatitis B virus (HBV) and other as defined in the protocol.

• 60

• A decrease in AFP level of more than 20% at the Cycle 3 assessment, or the last assessment for subjects that terminated treatment prior to the Cycle 3 assessment, as compared with baseline.

Otherwise, the statistical methods as described in the protocol will be adopted.

10 Protocol Deviations and Analysis Sets

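### Both SAPs omit, without declaring it, the protocol's worsening criterion for treatment-emergent AEs, so a screening-onset AE that worsens under a single record is missed by the TEAE tables

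*SAP*

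**What the plan says.** Protocol 8.5.4 says that the AE summaries cover "those events that are emergent during treatment having been absent pretreatment, or worsen relative to the pretreatment state", and it ties this to an onset-date window from the first dosing day to 33 days after the last dose. Protocol 7.4.1.3 states that AE reporting "begins when the subject is included into the trial (date of first signature of informed consent"), and screening may last up to 28 days, so AEs with onset before dosing will be in the database.

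The Phase Ib SAP, Section 17.1, has: "A TEAE is defined as an adverse event with a start date on or after the date of first dose of tepotinib". The Phase II SAP, Section 17.1, uses the same criterion: "an adverse event with a start date on or after the date of first dose of tepotinib". Both apply the 33-day limit and then relax it for later events that the investigator judges related, "in which case it is classified as a TEAE despite occurring more than 33 days after the last treatment administration". Both exclude a Day 1 event whose onset preceded the first dose. Neither mentions worsening.

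Section 9 of each SAP lists the changes from the protocol's planned analyses. The TEAE definition is in neither list, and both lists close with "Otherwise, the statistical methods as described in the protocol will be adopted". Both SAPs also state: "All analyses described in Section 17.1 will be based on TEAEs if not otherwise specified".

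**The concern.** The protocol's rule has two limbs, new events and worsened events, and the SAPs carry over only the first. Take an AE with onset on Day -10 that reaches Grade 3 on Day 20 and is kept as one record. Its start date precedes the first dose, so under either SAP it is not a TEAE.

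The tables affected are the main AE summaries of the report: any, related, serious, Grade 3 or higher, Grade 4 or higher, AESI, and AEs leading to discontinuation (permanent in both SAPs, temporary as well in Phase II). The rows and listing for TEAEs leading to death follow the same definition.

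This population is likely to have pre-dose events. Subjects have liver disease, undergo a mandatory pretreatment biopsy, and may have stopped sorafenib only 14 days before Day 1. Protocol 3.5 names hepatobiliary toxicity as a potential risk, and protocol 5.2 names the liver and bile ducts as the main target organ in the dog studies. Worsening of a hepatic or constitutional event that began before dosing is what the worsening limb exists to capture.

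**Working it through.** The point concerns a definition. The plan states no figure that depends on it, so there is nothing to reproduce. The check is to apply each rule to the same kinds of event.

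| Event | Protocol 8.5.4 | Both SAPs, 17.1 |
|---|---|---|
| New, onset after first dose, within 33 days of last dose | Counted | Counted |
| Onset in screening, does not worsen | Not counted | Not counted |
| Onset in screening, worsens, worsening entered as a separate AE with its own onset date | Counted | Counted |
| Onset in screening, worsens, kept as one record | Depends on what onset means | Not counted |
| Onset more than 33 days after last dose, judged related | Not counted | Counted |

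**Fourth row.** The protocol sentence reads "having been absent pretreatment, or worsen relative to the pretreatment state and with onset dates occurring within the first dosing day of study treatment", and the window then runs to 33 days after the last dose.

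1. If onset means the original onset, an event that worsens relative to its pretreatment state must have existed before dosing. Its onset then always lies outside the window, and the worsening limb could never add an event.
2. If onset means the onset of the worsening, the limb has effect and the single-record event counts.
3. The second reading is the only one that gives the worsening limb work to do within a single record. The alternative is that every worsening gets its own record (third row). Neither SAP states either rule.

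**Does the recording convention settle it?** Protocol 7.4.1.2 has unfavorable changes in condition recorded as AEs. Protocol 7.4.1.1 exempts conditions present at the initial visit only if they do not worsen. Neither says what to do with an AE that begins later in screening and then worsens. Section 7.4.1.2 refers detail to eCRF completion conventions that are not among the documents.

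**Which outputs depend on TEAE status?** Only the Section 17.1 analyses do. These do not:

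- laboratory worst-grade and shift tables, and eDISH plots (17.3)
- vital signs, ECG and ECOG (17.4 to 17.6)
- death tables, taken from the Death and Survival Follow-Up eCRFs (17.2.1)
- Phase Ib DLTs, taken from the flag on the AE form (Phase Ib SAP 16.1)

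The all-AE and all-SAE listings keep the event. By start date, however, the AE listing's period flag would mark it as before the treatment-emergent period.

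**Size.** One subject is 1/48 = 2.1 percentage points in Phase II and 1/12 = 8.3 points at 500 mg in Phase Ib. These are upper bounds per missed subject, because a subject with another qualifying event already counts in that row. The documents do not say how many subjects would be missed.

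**Fifth row.** The related-after-33-days extension is absent from protocol 8.5.4 and is also not listed in Section 9 of either SAP.

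**The case against.** The strongest reply is that the protocol itself requires an onset date inside the treatment window. Read literally, the single-record example fails the protocol rule too, and the SAPs merely apply its date condition. This stands to the extent that the protocol sentence is ambiguous. It does not dispose of the point, because the literal reading leaves the worsening limb with no effect.

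The second reply is that sites may open a new record when an AE worsens, in which case the SAP rule captures it. The visible recording text is compatible with that, and the conventions that would settle it were not supplied. The gap is therefore conditional and narrow: onset between consent and first dose, later worsening, one record.

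The third reply is that other outputs show the signal. A reader might infer that these events drop out of all safety reporting. The documents do not support that, as the unaffected outputs above show. Hepatic laboratory worsening in particular is covered by the grade-shift tables and eDISH plots. What those tables do not show is clinical worsening such as jaundice, encephalopathy, fatigue or abdominal pain.

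A reader might also attach a percentage of affected subjects. Nothing in the documents anchors one.

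Finally, protocol 7.4.1.2 asks for onset date, resolution date and severity, but not the date on which the grade changed. A rule that dates the TEAE at the worsening may not be derivable from a single record. This is correct, and the fix has to allow for it.

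**Conclusion.** The point holds in a limited form. Both SAPs omit the protocol's worsening criterion and neither declares the omission, although each says that the protocol's methods otherwise apply. Where a worsening is not entered as its own AE, the Section 17.1 TEAE tables and the listing of TEAEs leading to death will leave out screening-onset AEs that worsen on tepotinib.

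This rests on two assumptions: that onset in protocol 8.5.4 is meant to include onset of worsening, and that at least some worsenings are kept under the original record. The effect on AE counts cannot be sized from the documents. The primary endpoints are untouched: Phase II uses progression-free status and Phase Ib uses the DLT flag. The change is worth making because it is cheap and affects the headline AE summaries, but it does not amount to a loss of the safety data.

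**What to change.** In both SAPs:

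1. Extend the TEAE definition to AEs with onset before first dose whose grade or seriousness worsens between first dose and 33 days after last dose. Where the worsening has its own record, use that record.
2. Where there is only one record and no date of grade change, count a pre-dose AE that is ongoing at first dose as a TEAE if its recorded worst grade or seriousness exceeds its pre-dose state, or if that state cannot be determined. This leans the same way as the SAPs' existing convention of treating AEs with no recorded relationship as related.
3. State how sites record a worsening.
4. List the related-after-33-days extension in Section 9.

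In protocol 8.5.4, clarify that onset includes the onset of worsening.

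If the sponsor prefers to keep the start-date rule, it should be declared and justified in Section 9.

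The cost is a short addition to each SAP and a derivation rule with a single-record branch. TEAE counts may rise slightly, and the single-record branch may over-count a few events.
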